5. Instruct that the subject is to continue to avoid eating raw or undercooked hen eggs or food known to include raw or undercooked hen eggs. Subjects who tolerate the open baked whole egg food challenge without any dose-limiting symptoms will be instructed to introduce baked egg into their diet after screening per the Mount Sinai guidelines ([Lieberman, 2012](#)), or to continue their consumption of baked egg if consuming baked egg before the exit DBPCFC. Subjects who have dose-limiting allergy symptoms during the open baked whole egg food challenge will be instructed to avoid all forms of hen egg.
6. Schedule a follow-up study appointment according to the protocol.
7. Telephone the following day to inquire about post-open baked whole egg food challenge adverse events, and assist accordingly.

REFERENCES

Sampson HA, Gerth van Wijk R, Bindslev-Jensen C, Sicherer S, Teuber SS, Burks AW, et al. Standardizing double-blind, placebo-controlled oral food challenges: American Academy of Allergy, Asthma & Immunology-European Academy of Allergy and Clinical Immunology PRACTALL consensus report. *J Allergy Clin Immunol*. 2012;130(6):1260-74.

Appendix 3: Guidance on Study Conduct During a Pandemic, Epidemic, or Other Emergency Not Related to the Study

Table of Contents

1	INTRODUCTION	102
2	ENROLLMENT AND STUDY PROCEDURES	103
2.1	Recruitment, Screening, and Enrollment	103
2.2	Informed Consent.....	103
2.3	Duration of Study.....	104
2.4	General Study Visit Procedures	104
2.4.1	Initial Dose Escalation	105
2.4.2	Up-Dosing Period	105
2.4.3	Maintenance Period	106
2.5	Remote Unscheduled Visits	106
2.6	Early Discontinuation.....	106
2.7	Study Exit.....	107
2.8	Safety Follow-Up	107
3	TREATMENT COMPLIANCE.....	107
4	SAFETY CONSIDERATIONS	108
4.1	Dose Adjustment.....	108
4.2	Missed Doses	108
5	STATISTICAL METHODS	110
6	STUDY MONITORING	111

1 INTRODUCTION

In the event of a pandemic (eg, Coronavirus Disease 2019 [COVID-19] pandemic), epidemic, or other emergency not related to the study (eg, natural disaster, act of war or terrorism), restrictions may be issued at the country, state, regional, and/or local level that may affect study conduct, the scientific integrity of the study, or the safety and well-being of study participants and study site staff. When such restrictions and associated challenges (eg, site closures; travel restrictions; quarantines; pandemic- or epidemic-related illness in subjects, parents, caregivers, or study site personnel) prevent the conduct of study site visits (defined herein as a study visit that is conducted onsite at the study site, not remotely) and access to study product for an extended period, changes to certain study procedures will be implemented as described in this appendix and in accordance with regulatory requirements to ensure subject safety and continued treatment, care, and sponsor oversight.

Study sites must inform Aimmune (study sponsor) as soon as possible when such restrictions are issued or anticipated. Similarly, study sites must inform the sponsor when the restrictions are lifted. The resumption of study site visits will be determined in consideration of individual subjects; study sites; and local, state, regional, and national guidance as applicable; and in accordance with regulatory requirements.

The alternate procedures (also referred to as remote procedures) described in this appendix may be implemented for individual subjects; by study site; or at the local, state, regional, or national level as appropriate. As the ability to attend scheduled study site visits may change over time for individual subjects, study visits may alternate between remote procedures and study site visits as needed for flexibility until the restrictions are fully lifted and regular study site visits can resume. Additional details for the remote procedures will be provided in other supporting documents for study conduct. Procedures will be per protocol for subjects able to attend scheduled visits at the study site.

This appendix was prepared in consideration of the guidance released by the Food and Drug Administration (FDA Guidance on Conduct of Clinical Trials of Medical Products During COVID-19 Public Health Emergency updated 11 May 2020) and the European Medicines Agency (Guidance on the Management of Clinical Trials During the COVID-19 [Coronavirus] Pandemic version 3, 28 Apr 2020). As updates to these regulatory guidances are expected, the alternate procedures described in this appendix may be supplemented or superseded accordingly through supportive materials for study conduct as directed by the sponsor.

2 ENROLLMENT AND STUDY PROCEDURES

2.1 Recruitment, Screening, and Enrollment

The sponsor will notify study sites when recruitment, screening, and enrollment of subjects is suspended.

An exception to suspension of screening and enrollment is as follows: subjects who complete the screening open baked whole egg food challenge before remote procedures are implemented may return to the study site to complete the double-blind, placebo-controlled food challenge (DBPCFC) per protocol and enroll in the study if eligible. However, continued participation in the study will be per investigator and subject or parent/caregiver decision, based on the ability to attend study site visits and understanding the potential impact of the restrictions on study conduct.

2.2 Informed Consent

Study site personnel must obtain consent and assent (where required) before any remote procedures are conducted. Consent for remote procedures will include the release of contact information to allow the shipment of study product directly to the subject or designated responsible person's home or for study product to be picked up at the study site. Reconsent for other reasons (eg, protocol amendment, updated safety information) may be required during the restrictions.

The informed consent process (written; oral if the return of written consent for remote procedures is not possible) must be documented in the subject's source documents. Written consent is to be returned to the study site as soon as feasible for subjects who provided oral consent.

2.3 Duration of Study

The total duration of the study and duration of study treatment for individual subjects will be extended as needed to allow subjects to complete study treatment following delays due to the restrictions.

2.4 General Study Visit Procedures

Study visits will be conducted remotely (eg, telephone or video call) for subjects, parents, and caregivers who cannot attend scheduled visits at the study site due to the restrictions. Remote study visits will occur at the same intervals specified in the protocol schedules of activities.

On the day of a remote study visit, subjects will take their dose of study product at home per their usual dosing schedule.

During remote study visits, noninterventional visit procedures will be conducted according to the protocol schedules of activities as applicable and recorded in the subject's source documents:

- Adverse events review
- Concomitant medications review and instruction
- Treatment compliance/accountability review
- Diet/food allergen exposure review
- Food allergy instruction
- Peak expiratory flow (PEF) at investigator discretion
 - Protocol-required spirometry and PEF should be performed per local clinical practice guidelines during the restrictions. Precautions should be followed per clinical recommendations to decrease risks associated with aerosol generation and possible infectious spread. PEF may be done at home at investigator discretion if routine spirometry and/or PEF cannot be done at the study site due to the restrictions.
- Pregnancy review
 - In the absence of a pregnancy test, oral confirmation must be obtained that a female subject of childbearing potential is not pregnant. Subjects will be reminded to continue to use contraception and to notify the study site if concerned about pregnancy. A pregnancy test will be performed at the next study site visit.

Procedures that will not be completed during remote study visits are as follows:

- Weight, height, and vital signs measurements
- Questionnaires to assess atopic disease
 - Asthma Control Test (ACT)/Childhood-ACT (C-ACT)
 - Eczema Area and Severity Index (EASI)
 - Total Nasal Symptom Score (TNSS)
- Quality of life questionnaires
- Physical examinations
- Skin prick tests
- Blood sample collection
- Pregnancy tests
- Food challenges
 - Food challenges will be delayed until the restrictions are lifted and regular study site visits resume. Food challenges are to be completed within 3 months after regular study site visits resume for subjects who meet the protocol criteria for having a food challenge.

After completion of a remote study visit, study product will be dispensed as needed for dosing at home. Study site staff should confirm that study product was received by the appropriate individual.

After each remote study visit, site staff will contact the subject or parent/caregiver by telephone within 3 days. In addition to the standard telephone call queries, receipt of study product will be confirmed (if applicable). The telephone call is at investigator discretion when study product is not dispensed after a remote study visit and dosing is continued at the same dose level.

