9.3 Safety and Other Assessments

9.3.1 Lung Function Tests and Assessments of Asthma Control

Lung function tests will be performed according to the schedules of activities ([Appendix 4](#), [Appendix 5](#)). Lung function tests include PEF for subjects aged ≥ 6 years and attempts of PEF for subjects aged 4 to 5 years. Spirometry will be performed if PEF shows a clinically

relevant reduction or for symptoms of clinical deterioration (eg, active wheeze on physical examination). Spirometry will be performed at screening for subjects aged ≥ 6 years with asthma.

For subjects with asthma, the evaluation of asthma severity will be assessed using the classification in [Table 17](#).

Asthma control in subjects with pre-existing asthma will be assessed using scores from the Asthma Control Test (ACT) ([Schatz, 2006](#)) and by the incidence of asthma rescue medication use. The ACT is a self-administered, 5-item questionnaire for subjects aged ≥ 12 years, used to evaluate the level of asthma control in the last 4 weeks. Each question is presented on a 5-point scale, with lower numbers indicating worse asthma control. A composite score of more than 19 indicates well-controlled asthma.

The Childhood Asthma Control Test (C-ACT) is a 7-item questionnaire used to evaluate the level of asthma control in subjects aged 4 to 11 years with pre-existing asthma ([Liu, 2007](#)). Subjects complete the first part of the questionnaire, which consists of 4 questions and a choice of 4 responses from 0 (worse asthma) to 3 (controlled asthma) for each question. The parent/caregiver may help the subject read or understand the question if needed, but only the subject should select the response. The parent/caregiver completes the second part of the questionnaire, which consists of 3 questions and a choice of 6 responses from 0 (worse asthma) to 5 (controlled asthma) for each question. Parents/caregivers are asked to recall asthma symptoms in the last 4 weeks and complete their portion of the questionnaire without influence from the subject's responses. A composite score of more than 19 indicates well-controlled asthma.

Table 17: Evaluation of Asthma Based on NHLBI Criteria

Classification	Intermittent (Step 1)	Persistent: Mild (Step 2)	Persistent: Moderate (Step 3 or 4)	Persistent: Severe (Step 5 or 6)
Symptoms	≤ 2 days/week	> 2 days/week but not daily	Daily	Throughout the day
Night-time awakenings				
Subject aged 0-4 years	0	1-2 times/month	3-4 times/month	> 1 time/week

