2.6 Early Discontinuation

Subjects who discontinue early from the study while restrictions are in place will have a remote early discontinuation visit approximately 14 days after their last dose of study product. Noninterventional early discontinuation procedures will be conducted according to the protocol schedule of activities and as described in [Section 2.4](#). Subjects will be

encouraged to return to the study site to complete all early discontinuation procedures when regular study site visits resume, unless consent is withdrawn.

Subjects with unresolved adverse events at early discontinuation while restrictions are in place or who had gastrointestinal (GI) adverse events of interest will have safety follow-up ([Section 2.8](#)).

The criteria for early discontinuation due to missed doses while restrictions are in place will be based on the guidance provided later in this appendix ([Figure 1](#), [Table 1](#)). Depending on the reason and number of missed doses, certain subjects who miss doses and stop study product dosing when the restrictions are in place will not be discontinued early from the study. Such subjects may reinitiate dosing after study site visits resume. When regular study site visits resume, the regular protocol criteria for early discontinuation due to missed doses will apply.

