2.8 Safety Follow-Up

In the event remote procedures are implemented, safety follow-up procedures will be conducted in accordance with the study protocol, except that subjects who discontinue due to GI adverse events will have remote study visits instead of study site visits when required, and no symptom-directed physical examinations will be performed.

Subjects or parents/caregivers of subjects who had GI adverse events of interest will be asked to complete the Pediatric Eosinophilic Esophagitis Symptom Scores version 2.0 (PEESS v2.0) per protocol.

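### Remote visits drop self- or parent-completed questionnaires, so subjects who discontinue during restrictions have no FAQLQ/FAIM value after screening unless they later choose to return

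*Protocol*

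**What the plan says.** Appendix 3 Section 2.4 governs visits held by telephone or video during a pandemic or similar emergency. Under "Procedures that will not be completed during remote study visits are as follows" it places "Questionnaires to assess atopic disease" (ACT/C-ACT, EASI, TNSS) and "Quality of life questionnaires" beside skin prick tests, blood sampling, physical examinations and food challenges.

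Appendix 3 Section 2.6 says that subjects who discontinue during restrictions "will have a remote early discontinuation visit approximately 14 days after their last dose of study product". What is done there is limited to the noninterventional procedures of Section 2.4. Afterwards these subjects are "encouraged to return to the study site to complete all early discontinuation procedures when regular study site visits resume".

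Appendix 3 Section 2.7 keeps subjects who finish treatment on blinded product and holds their exit until onsite visits resume. Appendix 3 Section 2.8 says that subjects or parents of subjects with gastrointestinal adverse events of interest "will be asked to complete the Pediatric Eosinophilic Esophagitis Symptom Scores version 2.0 (PEESS v2.0) per protocol".

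In the Appendix 5 schedule, FAQLQ and FAIM are marked only in the early discontinuation/exit column. ACT/C-ACT, EASI and TNSS are also marked at the 80 mg and 300 mg visits.

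**The concern.** The excluded list mixes two kinds of procedure. Skin tests, blood samples, food challenges and the EASI, which scores clinical signs, need someone on site. ACT/C-ACT, TNSS, FAQLQ and FAIM need only an answer from the subject or parent, and a remote contact with that person is already taking place.

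The consequence falls on one group. A subject who discontinues during restrictions passes through the only FAQLQ/FAIM time point scheduled after screening without being asked the questions. A subject who completes treatment during the same restrictions is kept on treatment until the questions can be asked on site. Within the restricted period, whether a value exists therefore depends on whether the subject discontinued. Among the reasons for discontinuation in Section 5.3, Table 4 are poor tolerability and poor control of atopic disease, which these instruments may reflect. No analysis can recover a form that was never given.

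At stake are the exploratory changes from baseline in FAQLQ, FAIM, ACT/C-ACT and TNSS (Section 10.7) and the descriptive summaries of ACT, C-ACT and TNSS (Section 10.6).

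**Working it through.** The protocol states no figure on this point to reproduce. The check is mainly a comparison of sections, with simple arithmetic for timing and size.

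**1. Do the forms need a site?**
- ACT: Section 9.3.1 says "The ACT is a self-administered, 5-item questionnaire".
- C-ACT: the child answers the first part. For the rest, "The parent/caregiver completes the second part of the questionnaire" (Section 9.3.1).
- TNSS: subject recall over one week (Section 9.3.3).
- FAQLQ and FAIM: self-report, with proxy or parent forms (Section 9.4).
- EASI: a score of clinical signs (Section 9.3.2), so its place on the list is understandable.
- PEESS v2.0: also completed by subject or parent (Section 9.3.4), and kept under remote procedures.

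**2. Which values exist for each type of subject?**

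| Subject | FAQLQ/FAIM after screening | ACT/C-ACT, TNSS |
|---|---|---|
| Completes, with or without restrictions | Onsite exit | Onsite exit, plus the 80 mg and 300 mg visits |
| Discontinues, able to attend the site | Onsite early discontinuation visit | Same visit, plus 80 mg and 300 mg if reached on site |
| Discontinues during restrictions, remote visit | None unless the subject later returns | None at discontinuation unless the subject later returns; 80 mg and 300 mg if reached on site |

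The return visit is voluntary and undated. The 3-month limit in Appendix 3 Section 2.4 applies to food challenges only.

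**3. What would a day-14 value measure?** The early discontinuation visit is about 14 days after the last dose, whether onsite (Section 5.3) or remote.
- ACT, and the parent part of C-ACT, recall 4 weeks: 28 − 14 = 14 days of the window fall on treatment. Once 28 days or more have passed since the last dose, none do.
- TNSS recalls 1 week: the window runs from day 7 to day 14 after the last dose, so it contains no treatment days even at the ordinary visit.

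A remote day-14 value thus matches the onsite early discontinuation visit in timing. It is not an on-treatment value.

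**4. How many subjects?** Planned N = 84 (Section 10.3). The protocol gives neither a discontinuation rate nor the share falling in a restricted period, so both are assumed.
- Lower rate: the largest US egg oral immunotherapy trial described in Section 1.1 had 7 withdrawals before maintenance among 55 subjects, 7/55 = 12.7%. Then 0.127 × 84 ≈ 10.7 discontinue.
- Higher rate, an assumption: 20%, giving 0.20 × 84 = 16.8.
- Share during restrictions, an assumption: 25% to 75%.
- Lowest: 0.25 × 10.7 ≈ 2.7, about 3 subjects (3/84 ≈ 4%).
- Highest: 0.75 × 16.8 = 12.6, about 13 subjects (13/84 ≈ 15%).

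**5. Does the protocol indicate a direction of bias?** In the same trial, withdrawals before maintenance were 5/40 = 12.5% on active treatment and 2/15 = 13.3% on placebo. These figures give no ground for expecting more discontinuation on AR201.

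**The case against.** The strongest defence is that pausing exploratory scores in an emergency while keeping a safety form is a reasonable priority. PEESS v2.0 is given only to subjects with gastrointestinal events of interest, and the investigator reviews it for signs of eosinophilic esophagitis. C-ACT asks the child alone to choose the responses and the parent to answer uninfluenced, which is harder to ensure by mail or telephone. Remote procedures apply subject by subject, and anyone able to attend follows the normal schedule. Appendix 3 Section 5 leaves restriction-related changes of method to the statistical analysis plan.

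Part of this stands. The different purpose of PEESS explains why it was kept, so its retention shows feasibility and is not a contradiction. The C-ACT point is a real cost in data quality. The analysis plan can decide how values are used, but it cannot supply values that the visit procedures exclude.

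Three stronger readings are tempting and are not supported:
- A reader might infer that quality of life in this trial rests on completers. That is not so in general: discontinuers who can attend have an onsite FAQLQ/FAIM, and those who cannot may return later.
- A reader might infer bias in favour of AR201. The withdrawal figures in Section 1.1 are about equal between arms, and some losses during restrictions may be unrelated to treatment.
- A reader might want the day-14 value to serve as an end-of-treatment value. For TNSS it contains no treatment time, and for ACT only about half the window.

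**Conclusion.** The point holds, and it is minor. For subjects who discontinue during restrictions, the appendix excludes forms that could be completed remotely at the only FAQLQ/FAIM time point scheduled after screening, and offers in exchange a voluntary, undated return. Completers in the same period keep their exit value. The resulting dependence of missingness on discontinuation may bias the exploratory change-from-baseline comparisons, in a direction that the protocol does not allow one to state.

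The loss is firmest for FAQLQ and FAIM, which have no intermediate visit. For ACT/C-ACT and TNSS the loss is of a timely value at discontinuation. The range of about 3-13 of 84 subjects rests wholly on the assumed rates and is an illustration of scale. Primary and secondary endpoints are untouched.

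**What to change.** In Appendix 3 Sections 2.4 and 2.6, move FAQLQ, FAIM, ACT/C-ACT and TNSS to the procedures done at the remote early discontinuation visit, by mail, electronic form, telephone or video, and record the mode of completion. Keep EASI, skin prick test, blood samples, physical examination and other onsite measurements for the return visit. Label the result as the early discontinuation visit value, with the same nominal timing as the onsite visit, and do not treat it as on-treatment.

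The cost is small: forms are added to a contact that already takes place. The downside is that some values will differ in mode of administration, with C-ACT the most sensitive because child and parent must answer independently. Recording the mode lets this be examined.

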2.4.1 Initial Dose Escalation

Subjects who completed day 1 but not day 2 of initial dose escalation at the time remote procedures were implemented will stop study product dosing until regular study site visits resume. When study site visits resume, day 1 of initial dose escalation will be repeated following discussion and approval from the medical monitor ([Section 4.2](#)).

2.4.2 Up-Dosing Period

The duration of up-dosing for individual subjects will be extended to accommodate any delays due to the restrictions.

Subjects in the up-dosing period of study treatment will continue daily dosing with study product at their current dose level until the next study site visit. Dose adjustments may be allowed ([Section 4.1, Table 1](#)). No up-dosing will be allowed until the next study site visit.

When study site visits resume, study treatment will continue or resume under medical supervision at the study site as follows:

- Subjects who continued dosing at their current dose level or a lower dose level may resume up-dosing to the next dose level at the study site per protocol.
- Subjects who stopped study product and did not discontinue from the study may reinitiate dosing at the study site following approval from the medical monitor as described in [Section 4.2, Table 1](#), and [Table 2](#).

2.4.3 Maintenance Period

The duration of maintenance treatment for individual subjects will be extended as needed to accommodate any delays due to the restrictions.

Subjects in the maintenance period of study treatment will continue daily dosing at their current dose level of study product until study site visits resume. Dose adjustments may be allowed ([Section 4.1, Table 1](#)).

When study site visits resume, study treatment will continue or resume under medical supervision at the study site as follows:

- Subjects who continued daily dosing at 300 mg/day may continue their maintenance treatment regimen per protocol.
- Subjects who had dose reductions during the maintenance period will follow dose re-escalation procedures per protocol.
- Subjects who stopped study product and did not discontinue from the study may reinitiate dosing at the study site following approval from the medical monitor as described in [Section 4.2, Table 1](#), and [Table 2](#).

